APPENDIX 6: IWQOL-KIDS

The subject will answer questions based on what best applies to them in the past seven days. Each question contains five response options: “always true”, “usually true”, “sometimes true”, “rarely true”, and “never true”, scaled from 1 to 5, respectively.

Physical Comfort

1. Because of my weight I avoid using stairs whenever possible.
2. Because of my weight it is hard for me to bend over to tie my shoes or to pick something up off the floor.
3. Because of my weight it is hard for me to move around.
4. Because of my weight it is hard for me to fit into seats in public places (e.g. movie theaters, desks at school, and booths in restaurants).
5. Because of my weight my knees or ankles hurt.
6. Because of my weight it is hard for me to cross my legs.

Body Esteem

7. Because of my weight I am ashamed of my body.
8. Because of my weight I don't like myself very much.
9. Because of my weight I try not to look at myself in mirrors or in photographs.
10. Because of my weight I have a hard time believing compliments that I receive from others.
11. Because of my weight I am lacking in self-confidence.
12. Because of my weight I avoid activities that involve wearing shorts or a bathing suit.
13. Because of my weight it is very difficult for me to buy clothing.
14. Because of my weight I don't like to change my clothes or undress in front of others.
15. Because of my weight I am embarrassed to try out for activities at school.

Social Life

16. Because of my weight people tease me or make fun of me.
17. Because of my weight people talk about me behind my back.
18. Because of my weight people avoid spending time with me.
19. Because of my weight people stare at me.
20. Because of my weight I have trouble making or keeping friends.
21. Because of my weight people don't think I'm very smart.

Family Relations

22. Because of my weight family members treat me differently from the way they treat other people.
23. Because of my weight family members talk about me behind my back.
24. Because of my weight one or more people in my family reject me.
25. Because of my weight my parents aren't proud of me.
26. Because of my weight family members make fun of me.
27. Because of my weight family members don't want to be seen with me.

APPENDIX 7: FORMULAS FOR ESTIMATING CREATININE CLEARANCE

Creatinine clearance in adolescent boys and girls should be calculated based on height (HT) and serum creatinine (sCr) using the Schwartz formula (refs) as noted below.⁷

$$CrCl_{adolescent\ boy} = \frac{[0.70 \times Ht(cm)]}{sCr \left(\frac{mg}{dL} \right)}$$

$$CrCl_{adolescent\ girl} = \frac{[0.55 \times Ht(cm)]}{sCr \left(\frac{mg}{dL} \right)}$$

APPENDIX 8: SUMMARY OF CHANGES IN AMENDMENT #1

Amendment #1 (05 October 2018)

Rationale:

This protocol amendment is being implemented to clarify or revise several inconsistencies that had been noted in the original version. This amendment does not involve substantive changes to the subject population or additional study procedures, and is not expected to have any impact on the safety of study subjects. Specific changes are noted by section in the following table.

Section and/ or Item	Changes Effected
Header	Updated protocol version and version date.
Title Page	Added new line for Amendment 1 and version date.
Investigator Signature Page	Updated protocol version and version date.
Section 1.0: Table of Contents	Updated Table of Contents
Section 2.0: Protocol Synopsis – Study Objectives	Text deleted: "...VI-0521 (PHEN/TPM 7.5 mg/46 mg and PHEN/TPM and 15 mg/92 mg doses) for..."
Section 7.2: Exclusion Criteria #14	Text deleted: "Any history of any -eating disorders (e.g. bulimia; binge eating disorder; anorexia);"
Section 8.4.1: Formulation and Packaging	Revised: "...during the first 4 weeks of study treatment and the first 4 weeks following up-titration for subjects randomized to the top dose (titration period during study Weeks 13-16) , and treatment kits (bottles), for use once subjects have been titrated to their assigned dose."
Section 8.4.3: Administration	Revised: "...should the next study visit be scheduled after Week 4 beyond 4 weeks after the previous visit . Investigators will..."
Section 9.1: Screening Visit (Visit 1, Up to – 4 Weeks)	Added: "Administer neurocognitive battery (CANTAB) familiarization session"
Section 9.1.3: Treatment Week 4 Through Week 52 (Visits 3 Through 15)	Revised: "Administer neurocognitive battery (CANTAB), Visit 36 only;"
Section 9.2: Study Period	Revised: "...Sites should link the scheduling of visits to the baseline /randomization visit (Visit 2, Day 0). ... so that the overall treatment duration is 56 days weeks for subjects..."
Section 10.10: Oral Glucose Tolerance Test	Revised: "An oral glucose tolerance test (OGTT) will be obtained at baseline Visit 2 (after results from Visit 1 screening visit indicate the subject ...")

Section and/ or Item	Changes Effected
Section 10.11: CANTAB (Cambridge Neuropsychological Test Automated Battery)	Revised: “An oral glucose tolerance test (OGTT) will be obtained at baseline Visit 1 Visit 2 (after results from Visit 1 screening visit indicate the subject ...”
Section 10.12: IWQOL- Kids	Revised: “... is a 27-item, self-administered instrument that will be completed at baseline (Visit 2), Visit 9 (Week 28) and end of study (Visit 16 at Week 56 or early termination).”
Appendix 1: Schedule of Events	
Updated CANTAB test to add familiarization test to Screening and moved test at Week 4 to Week 16.
 
Text added to “Contraception/Pregnancy Counseling”
 
Added “Schedule Next Visit”
 
Added footnote c.

Appendix 1: Schedule of Events	
Updated CANTAB test to add familiarization test to Screening and moved test at Week 4 to Week 16.
 
Text added to “Contraception/Pregnancy Counseling”
 
Added “Schedule Next Visit”
 
Added footnote c.

Section 19.0: References	Updated References #1, #3, #5, #6.
Appendix 1: Schedule of Events	
Updated CANTAB test to add familiarization test to Screening and moved test at Week 4 to Week 16.
 
Text added to “Contraception/Pregnancy Counseling”
 
Added “Schedule Next Visit”
 
Added footnote c.

APPENDIX 9: SUMMARY OF CHANGES IN AMENDMENT #2

Amendment #2 (21 June 2019)

Rationale:

This protocol amendment is being implemented to clarify or revise several inconsistencies that had been noted in the previous version. This amendment does not involve substantive changes to the subject population or additional study procedures, and is not expected to have any impact on the safety of study subjects. Specific changes are noted by section in the following table.

Section and/ or Item	Changes Effected
Header	Updated protocol version and version date.
Title Page	Updated current and previous protocol version and version date.
Investigator Signature Page	Updated protocol version and version date.
Section 1.0: Table of Contents	Updated Table of Contents
Section 2.0: Protocol Synopsis – Study Rational	Text updated: “Obesity remains a major problem in pediatrics. National Health and Nutrition Examination Survey (NHANES) data indicate that 17.0 ^{18.5} % of children and adolescents age 2 to 19 years and 20.5 ^{20.6} % of adolescents age 12 to 19 years met the definition of obesity in 2011–2014 ^{2015–2016}”
Section 2.0: Protocol Synopsis – Study Design	Text revised: “...Randomization will be stratified by age (12-14 vs 15- 17 ¹⁶ years old) and gender....”
Section 2.0: Protocol Synopsis – Study Population: Key Exclusion Criteria	Text added: “...History of bipolar disorder or psychosis, greater than one lifetime episode of major depressive disorder , depression of moderate or greater severity...”
Section 4.0: Background	Text updated: “Obesity remains a major problem in pediatrics. National Health and Nutrition Examination Survey (NHANES) data indicate that 17.0 ^{18.5} % of children and adolescents age 2 to 19 years and 20.5 ^{20.6} % of adolescents age 12 to 19 years met the definition of obesity in 2011–2014 ^{2015–2016}”
Section 6.0: Study Design	Text revised: “...Randomization will be stratified by age (12-14 vs 15- 17 ¹⁶ years old) and gender....”
Section 7.2: Exclusion Criteria #9-27	Updated numbering.
Section 7.2: Exclusion Criteria #13	Text added: “Any history of bipolar disorder or psychosis, greater than one lifetime episode of major depressive disorder , current depression of moderate or greater severity...”
Section 8.2: Allocation to Treatment	Text revised: “...Randomization will be stratified by gender and age (12-14 vs 15- 17 ¹⁶ years old), and...”
Section 11.3: Reporting Period	Text revised: “The reporting period for adverse events begins when the subject provides written informed consent and extends until 28 calendar days after the last dose of the investigational product is administered day of study participation”

Section and/ or Item	Changes Effected
Appendix 1: Schedule of Events	Revised table header and footer.

## Version History

Version #	Description of Changes	Version Date
Final 1.0	Original Version	01Sept2020
1.1	Updates to Sections 5.2 and 6	07Jan2021

## Glossary of Abbreviations

Abbreviations pertain to the SAP only (not the TFLs).

Abbreviation	Term
AE	Adverse event
ANCOVA	Analysis of Covariance
ATC	Anatomical Therapeutic Chemical
BMI	Body Mass Index
BP	Blood Pressure
BMD	bone mineral density
BMC	bone mineral content
CANTAB	Cambridge Neuropsychological Test Automated Battery
CI	Confidence Interval
CRF	Case report form
C-SSRS	Columbia Suicide Severity Rating Scale
DXA	Dual-energy X-Ray Absorptiometry
ECG	Electrocardiogram
ET	Early Termination
HR	Heart Rate
LSD	protected Least Significant Difference
ITT	Intention-to-treat
IWQOL-Kids	Impact of Weight on Quality of Life-Kids
LOCF	Last observation carried forward
MAR	missing at random
MCMC	Markov chain Monte Carlo
MedDRA	Medical Dictionary for Regulatory Activities
mITT	Modified Intention-to-treat
MMRM	Mixed Effects Model with Repeated Measures
MNAR	missing not at random
PHQ-9	Patient Health Questionnaire-9
SAE	Serious Adverse Event
SD	Standard Deviation
SOC	System Organ Class
TEAEs	Treatment-Emergent AEs
TFLs	Tables, Figures and Listings

## **STATISTICAL ANALYSIS PLAN AMENDMENT 1**

Not applicable.

## 1. Source Documents

The Statistical Analysis Plan (SAP) was written based on the following documentation:

Document	Date	Version
Protocol	24 Aug 2017	Original
Protocol Amendment #1	05 Oct 2018	Amendment # 1
Protocol Amendment #2	21 Jun 2019	Amendment # 2
<e>CRF	17 Sep 2019	3.0
DMC Charter	27 Feb 2020	1.0
DMC Charter Amendment	NA	NA

## 2. Protocol Details

### 2.1 Study Objectives

The primary objectives are to evaluate the safety and efficacy of VI-0521 for the treatment of obesity in adolescents. The secondary objective is to characterize changes in obesity-related risk factors.

### 2.2 Overall Study Design

In this multicenter, randomized, double-blind, placebo-controlled, parallel-design study, approximately 200 subjects will be enrolled at approximately 20 sites in the United States. Subjects will be randomly assigned in a 1:1:2 ratio to placebo, N= 50; mid-dose (PHEN/TPM 7.5 mg/46 mg), N= 50; or top-dose (PHEN/TPM 15 mg/92 mg), N =100, of VI-0521, to be taken orally once daily in the morning. Randomization will be stratified by age (12-14 vs 15-16 years old) and gender. The study will consist of a screening period of up to 28 days, followed by a 56-week treatment period.

[figure not shown]
Subjects will be instructed to follow a mild hypocaloric diet modification program representing a 500-calorie/day deficit and to implement a family-based lifestyle modification program for adolescents, as tolerated, throughout the study period. The lifestyle program will include physical activity, behavior change, and family support. The same lifestyle modification program, specific to this population, will be implemented across all sites. Study drug will be titrated according to the following schema.

Group	Treatment Dosage for PHEN/TPM (mg)	Titration Dose for PHEN/TPM (mg)			
		Weeks 1-2	Weeks 3-4	Weeks 13-14	Weeks 15-16
Placebo	0/0	0/0	0/0	0/0	0/0
VI-0521 Mid	7.5/46	3.75/23	7.5/46	7.5/46	7.5/46
VI-0521 Top	15/92	3.75/23	7.5/46	11.25/69	15/92

Subjects who are unable to tolerate the assigned dose may be treated at a reduced dose level or may take a drug holiday as defined in the protocol. In addition, for growth monitoring, investigators will monitor rates of weight loss in treated subjects. For subjects with baseline BMI 95-98th percentile, reduce study drug dosage when BMI is < 85th percentile or when weight loss exceeds an average of 2 lbs (0.9 kg) per week. For subjects with baseline BMI  $\geq$  99th percentile, reduce study drug when weight loss exceeds an average of 2 lbs (0.9 kg)/week.

All subjects will return at approximately 4-week intervals for study assessments. All female subjects will undergo a pregnancy test at each visit. Subjects who discontinue study drug during the study will be encouraged to remain on study (off study drug) for continued follow-up by attending all remaining visits and have all study-related procedures performed, and to return at the 56-week time point for measurements and evaluations. For those who choose to completely withdraw from the study at any point, the end of study (Week 56) procedures should be completed.

**Figure 1. Schematic Diagram of Study Design**

## 2.3 Sample Size and Power

In previous studies in adults, VI-0521 mid-dose (PHEN/TPM 7.5 mg/46 mg) resulted in a placebo-subtracted BMI reduction of 2.4 units with a standard error approximately 0.16 units and a within treatment standard deviation of 2.9. A very conservative estimate of the treatment difference between the mid-dose and placebo would be 2 units of BMI which represents more than 2 standard errors below what was observed before. If we enroll 200 subjects (50 placebo, 50 mid-dose, and 100 top-dose), we will have at least 90% power to detect a statistically significant difference between the top-dose (PHEN/TPM 15 mg/92 mg) and the placebo because we could assume that the top-dose will have a higher effect size than the mid-dose. This calculation assumes that there will be an approximately 30% dropout rate. This sample size will also provide approximately 80% power to detect a statistically significant difference between the mid-dose and placebo.

## 3. Efficacy and Safety Variables

### 3.1 Primary Efficacy Endpoints

- The mean percent change in BMI from baseline to end of study (Week 56).

### 3.2 Secondary Efficacy Endpoints

- Percent of subjects achieving a reduction  $\geq 5\%$ ,  $\geq 10\%$  and  $\geq 15\%$  of baseline BMI at Week 56;
- Change from baseline in waist circumference at Week 56;
- Change from baseline in fasting insulin and Whole Body Insulin Sensitivity Index (Matsuda) at Week 56;
- Percent change from baseline in triglycerides and HDL-C at Week 56;
- Change from baseline in blood pressure at Week 56.

### 3.3 Exploratory Endpoints

- Evaluate effects of treatment on Impact of Weight on Quality of Life-Kids (IWQOL-Kids) questionnaire scores.
- Changes in various glycemic and lipid markers.
- Change in BMI Z-score.

### 3.4 Safety Endpoints

Safety will be assessed by evaluating adverse events (AEs)/serious adverse events (SAEs); vital signs, laboratory parameters (screening, periodically during the study and end of study); electrocardiograms; physical examinations; cognitive function tests using the Cambridge Neuropsychological Test Automated Battery (CANTAB). All subjects will be screened for the presence and severity of depression using the PHQ-

9: Modified for Teens and for suicidal/ideation using the Columbia Suicide Severity Rating Scale (C-SSRS) and follow up assessments will be done at each visit after treatment has been initiated. Bone age (X-ray of the hand and wrist) will be evaluated at baseline and end of study or early termination. Effect on bone mineral density and bone mineral content, as evaluated by Dual-energy X-Ray Absorptiometry (DXA) will be performed at baseline, end of study or early termination, at selected sites.

### **3.5 DXA (Sub Study)**

A bone health sub-study will be conducted at selected sites in approximately 100 subjects (25 each on placebo and mid-dose, and 50 on top-dose) to assess the effect of VI-0521 administration on bone health using Dual X-ray Absorptiometry (DXA). DXA scans of the posterior-anterior (PA) spine (lumbar), and total body less head (TBLH) will be performed at baseline and at the end of study or early termination. Equipment and procedures used to obtain DXA data will be standardized as described in a separate document. Sites involved in DXA measurement will be trained on these procedures prior to performing scans on study subjects. Scans will be read at a central facility and the reader will be blinded.

The following enrollment criteria will apply:

- 1) Both male and female will be eligible to participate;
- 2) Subjects with a history of any non-traumatic fracture will not be eligible;
- 3) Subjects with juvenile osteoporosis at baseline will not be eligible; and
- 4) Subjects must meet manufacturer equipment specifications with regard to height and weight limitations.

## **4. Analysis populations**

### **4.1 Randomized**

This population will be comprised of all subjects who were initially randomized. This population will be used for summaries of subject disposition and baseline subject characteristics.

### **4.2 Safety**

This population will be comprised of all subjects who were initially randomized and received at least one dose of study drug. This will be the primary population for all summaries of subject disposition and baseline characteristics, and safety analyses for purposes of regulatory submissions. The safety population is based on the treatments actually received.

### 4.3 Intent-to-treat (ITT)

This population will be comprised of all subjects who were initially randomized and received at least one dose of study drug. This will be the primary population for all summaries of efficacy analyses for purposes of regulatory submissions. The ITT population is based on the randomized treatments.

### 4.4 Modified Intent-to-treat (mITT)

This population will be comprised of all randomized study subjects who receive study treatment and return for at least one post-randomization assessment of height and weight. This population will be used for the analysis of all efficacy variables for all other purposes, including but not limited to publications, presentations, and robustness of sensitivity of analyses.

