12.3 Analysis Populations

Three different analysis populations will be used for analysis of data from this study, as described below:

- Randomized: This population will be comprised of all subjects who were initially randomized. This population will be used for summaries of subject disposition and baseline subject characteristics.
- Intent-to-treat (ITT)/Safety: This population will be comprised of all subjects who were initially randomized and received at least one dose of study drug. This will be the primary population for all summaries of subject disposition and baseline characteristics, efficacy analyses, and safety analyses for purposes of regulatory submissions.
- Modified Intent-to Treat (m-ITT): This population will be comprised of all randomized study subjects who receive study treatment and return for at least one post-randomization assessment of height and weight. This population will be used for the analysis of all efficacy variables for all other purposes, including but not limited to publications, presentations, and robustness of sensitivity of analyses.

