After such imputation, comparisons in the primary endpoint of change from the baseline BMI between treatment groups be assessed for the ITT population using a mixed effects model with repeated measures (MMRM) with factors of treatment, visit, treatment by visit interaction, baseline BMI value, age stratification, and gender stratification. Appropriate contrast will be applied for treatment comparisons at Week 56. The pairwise comparisons of interest are top-dose vs. placebo, and mid-dose vs. placebo, and top-dose vs. mid-dose. The primary null hypothesis will be that there is no treatment difference between any VI-0521 treatment groups and the placebo in the percent change from baseline to Week 56 in BMI. An appropriate contrast will be used for the comparisons at Week 56. The family-wise type 1 error for the comparisons will be controlled by Fisher's protected least significant difference (LSD) method at the 0.05 significance level: placebo, mid-dose, and top-dose will be first compared for overall difference in the percent change from baseline in BMI. Once the overall difference is significant at the 0.05 significance level, the above 3 pairwise comparisons will be conducted using Fisher's LSD method at the 0.05 significance levels. The order for comparisons of interest is top-dose vs. placebo, mid-dose vs. placebo, and top-dose vs. mid-dose. Due to the fact that only three treatments are compared, the above procedure strongly controls the family-wise type 1 error.

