Secondary efficacy endpoints that are continuous variables (change from baseline in waist circumference, fasting insulin, whole body insulin sensitivity index (Matsuda), triglycerides, HDL-C, and systolic and diastolic blood pressure) will be analyzed by a similar MMRM model as for the primary endpoint where the baseline BMI value will be replaced by the baseline value of the corresponding endpoint as a covariate.

The above analyses will be conducted for both the ITT and mITT populations.

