### 6.6.3 Sensitivity Analysis

The MMRM method used for the analysis will be applied to the mITT population with the observed data without imputation. The following sensitivity analyses will also be considered to explore the impact of missing data on the conclusion of the primary analysis.

The first sensitivity analysis is using a multiple imputation method based on the monotonic missing pattern under the assumption of MAR. The intermittent missing data will be imputed using multiple imputation MCMC procedure.

The second sensitivity analysis is also using multiple imputation, however, under the assumption of MNAR to explore the validity of MAR using pattern-mixture model:

1) For subjects who discontinue study participation prior to Week 56 and do not have follow-up visit, the missing data will be imputed using the observed data from the subjects in the same arm who discontinue the study treatment but have the primary endpoint measurement in the follow up visit using a regression method. The

intermittent missing data will be imputed using multiple imputation MCMC procedure. An ANCOVA model using a similar mixed procedure (without the repeated measures) as the primary analysis will be applied to these multiple-imputed % change in BMI at Week 56 with treatment, baseline BMI value as a covariate, and age and gender as stratification factors. The results of ANCOVA analysis on the multiple imputed datasets will be combined and summarized.

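### Protocol 12.3 and SAP 4.3–4.4 choose the efficacy population by audience: published results are assigned to mITT, whose specified MMRM also handles missing data differently from the ITT primary analysis

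*SAP*

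**What the plan says.** SAP 4.3 defines ITT as randomised subjects who took at least one dose, analysed as randomised, and adds: "This will be the primary population for all summaries of efficacy analyses for purposes of regulatory submissions". SAP 4.4 defines mITT as "all randomized study subjects who receive study treatment and return for at least one post-randomization assessment of height and weight", and gives its use: "This population will be used for the analysis of all efficacy variables for all other purposes, including but not limited to publications, presentations". That sentence goes on to name robustness or sensitivity work as a further use. Protocol 12.3 makes the same division, with m-ITT used "for all other purposes, including but not limited to publications, presentations, and robustness of sensitivity of analyses".

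The two sets then meet different analyses:

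- **Primary analysis.** SAP 6.6.1 first imputes missing values from retrieved dropouts or, if there are too few, by the washout method. It continues: "After such imputation, comparisons in the primary endpoint of change from the baseline BMI between treatment groups be assessed for the ITT population".
- **mITT analysis.** SAP 6.6.3 opens with: "The MMRM method used for the analysis will be applied to the mITT population with the observed data without imputation". It ends by promising similar primary-endpoint analyses for mITT, without saying which mITT analysis is the one for publication.
- **Secondary endpoints.** SAP 6.6.2 says: "The above analyses will be conducted for both the ITT and mITT populations".

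Protocol 18.0 leaves publication of results to the Clinical Trial Agreement with each site, which is not part of these documents.

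**The concern.** Membership of mITT depends on something that happens after randomisation and after dosing starts: coming back to be measured. Tolerability, motivation and perceived benefit can all influence that, so the arms of the mITT set are not guaranteed to be comparable as the randomised arms are. A plan that gives one population to regulators and another to journals and conferences invites two headline results from one trial, with the public one coming from the less protected set.

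A second difference sits on top of the first. The SAP's primary analysis imputes outcomes for subjects who leave. The mITT analysis that SAP 6.6.3 specifies does not. A reader of a publication could see an estimate that differs from the pre-specified primary one in both respects and have no way to tell which of them caused the gap.

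**Working it through.** **Step 1. The plan's own figure.** Protocol 12.2 and SAP 2.3 assume a difference of 2 BMI units, a within-treatment SD of 2.9, 50/50/100 subjects and about 30% dropout, which leaves 35/35/70.

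- Mid-dose vs placebo: SE = 2.9 × √(1/35 + 1/35) = 0.693, and 2/0.693 = 2.89. Two-sided 5% power by the noncentral t is 81.2% (stated: approximately 80%).
- Top-dose vs placebo: SE = 2.9 × √(1/70 + 1/35) = 0.600, and 2/0.600 = 3.33. Power is 91.0% (stated: at least 90%).

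The stated power reproduces. It does not decide this point, but the standard errors give a scale for what follows.

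**Step 2. When the choice of population matters.** In an MMRM on observed data, a subject with no post-baseline value contributes no outcome, so ITT and mITT give essentially the same estimate. The populations separate once outcomes are imputed. In the SAP 6.6.1 primary analysis, treated subjects who never returned enter ITT with imputed values and are absent from mITT. Summary percentages are also affected, because the default denominator in SAP 6.1 is the size of the relevant analysis population.

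**Step 3. Size of the population effect alone.** The documents give no rate of treated subjects without any later height and weight, so q below is an assumption. Suppose never-returned active subjects average the same as placebo, which is the logic of the washout fallback. Then ITT difference = (1 − q) × mITT difference, and for a true ITT difference of 2.0 the mITT difference is 2.0/(1 − q):

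| Assumed q | 1/(1 − q) | mITT difference | Excess |
|---|---|---|---|
| 2% | 1.020 | 2.04 | 0.04 |
| 5% | 1.053 | 2.11 | 0.11 |
| 8% | 1.087 | 2.17 | 0.17 |

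Against the standard errors in step 1, this runs from 0.04/0.693 = 6% to 0.17/0.600, or about 29%, of one SE. The illustration is in BMI units because the sample-size section is; the primary endpoint is percent change in BMI.

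**Step 4. Size of the missing-data difference.** This acts on everyone without Week 56 data, not only on never-returners. As an illustrative extreme, also an assumption, let all of the planned 30% lack Week 56 data, let the washout method apply, and let the observed-data MMRM give 2.0. The ITT estimate after washout imputation is then about 2.0 × (1 − 0.30) = 1.4. The gap of 0.6 units is between 0.6/0.693 = 0.87 and 0.6/0.600 = 1.0 standard errors. Week 56 data retrieved from subjects who stopped treatment would narrow it, as would retrieved-dropout imputation if those subjects keep some benefit.

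**Step 5. The protocol's wording does not settle it.** Protocol 12.5.1 places the primary MMRM on ITT. Protocol 12.5.2, describing the same MMRM, says it is applied to m-ITT on observed data. The role of mITT is therefore blurred in the protocol as well as divided by audience.

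**The case against.** The case on the other side has real force.

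- **ITT is already the primary analysis.** Protocol 12.5.1 and SAP 6.6.1 put the primary comparison on ITT with no qualification by audience, secondary endpoints are run on both sets, and SAP 6.6.3 uses mITT largely for sensitivity work. Nothing bars publication of the ITT result. This stands. It limits the point to which result the plan assigns to public use; the control of inference is not affected.
- **mITT excludes few people.** One later height and weight at any time is enough. Protocol 9.1.4 measures both at early termination, protocol 7.3 encourages off-drug visits, and it asks withdrawn subjects back at about Week 56 for height and weight at a minimum. Most early leavers could therefore stay in mITT. This stands.
- **The direction is not known.** A reader might infer that mITT drops subjects who could not tolerate active drug and so favours it. The documents give no non-return rate by arm and no link between early intolerance and failure to return. Placebo subjects may also leave, for lack of effect. That inference is not supported.
- **The arithmetic in step 3 fits only the fallback.** The SAP's first choice is retrieved-dropout imputation, under which non-returners may keep some benefit and the gap shrinks. This stands.
- **ITT is itself conditional on one dose.** True, but under double-blinding that is a lesser selection than returning for measurement.

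None of this removes the explicit rule in SAP 4.4 and protocol 12.3, which names publications and presentations as uses of mITT, and no passage says that ITT must lead there.

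**Conclusion.** The point holds in a limited form. Both documents select the efficacy population by audience and assign the public result to a set defined after randomisation. The MMRM that SAP 6.6.3 specifies for that set omits the imputation on which the ITT primary analysis depends. The published and primary estimates could therefore diverge for two reasons at once.

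The population effect alone is probably small: 0.04–0.17 BMI units on a true 2.0, if 2–8% never return and gain no benefit. Both conditions are assumptions, and the sign is not established. The missing-data difference is the larger risk. Its illustrative extreme of 0.6 units rests on the full 30% lacking Week 56 data and on the washout fallback.

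It would go too far to say that the published effect must rest on mITT alone or is known to be inflated. The ITT result will exist, its publication is not prohibited, and the site agreements that govern publication are not available here. The change should be made, but it does not threaten the validity of the primary analysis.

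**What to change.** In protocol 12.3 and SAP 4.3/4.4, replace the division by audience with three statements:

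1. The ITT analysis with its primary imputation (SAP 6.6.1) is the headline efficacy result for every use, including publications and presentations.
2. mITT is a sensitivity analysis only.
3. The number of subjects excluded from mITT is reported by arm.

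The m-ITT sentence in protocol 12.5.2 should be aligned with 12.5.1 at the same time.

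The cost is wording only. The ITT outputs are already planned, no new data are needed, and sample size and power are unchanged.
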